## Statistical Analysis Plan

#### 7.2. KEY DEFINITIONS

#### 7.2.1. First Dose Date

First dose date in the study is defined as the first dose of TAS-120 in Cycle 1.

## 7.2.2. Cut-Off Date of Final Analysis

For the purpose of final analysis, the cut-off date is defined as the date which all patients either discontinue from the treatment or have sufficient follow-up (more than 6 months) from the date of the first day of treatment with TAS-120 of the last patient enrolled, whichever occurs first.

#### 7.2.3. Last Dose Date

For the purpose of analysis, the last dose date is defined as the last dose date of TAS-120 for the patient or the cut-off date of final analysis, whichever occurs first.

## 7.2.4. Study Day

The study day in the study is the days relative to the first dose date in the study, while the cycle day is the days relative to the first dose date in that cycle.

#### 7.2.5. Treatment Duration

The overall treatment duration is defined as last dose date - first dose date+1.

#### 7.3. MISSING DATA

Missing data will not be imputed. Complete missing or partial date will be presented in the listings as reported on CRFs.

If an AE has a completely missing onset date, then the AE will be considered a TEAE. A medication with a completely missing start date is considered a prior medication. A medication with a completely missing stop date is considered a concomitant medication.

If an adverse event or a medication has a partial missing start or stop date, the following rules will be used to determine whether it is an AE or a TEAE, or a prior or concomitant medication.

CC

Sponsor: Taiho Oncology, Inc. Protocol: TPU-TAS-120-101

Version: 3.3, Phase 1 Dose Escalation Only

## Statistical Analysis Plan

Table 4: Partial Date Imputation for TEAE Determination

Partial Missing Start or Stop Date	Derived Start Date	Imputed Stop Date
Missing month and day, and the year is present	January 1 of that year or first dose date if the year is the same as the year of first dose date	December 31 of that year
Missing day, but year and month are present	First day of that month or first dose date if the year and month are the same as the year and month of first dose date	Last day of that month
Missing month, but year and day are present	Missing month derived as January or same as first dose month if the year is same as the year of first dose.	Missing month imputed as December

The above rule is also used for determining the cycles of adverse events and concomitant medications.

The derived date is only used for determining TEAEs, cycle of adverse events and concomitant medications. The collected partial dates will be reported in the listings.

Sponsor: Taiho Oncology, Inc. Protocol: TPU-TAS-120-101

Version: 3.3, Phase 1 Dose Escalation Only

Statistical Analysis Plan

# 8. DEMOGRAPHIC, OTHER BASELINE CHARACTERISTICS AND MEDICATION

#### 8.1. SUBJECT DISPOSITION AND WITHDRAWALS

The number of patients in each study population will be summarized along with the reason for exclusion from the population. In addition, patients' status with regard to study treatment and follow-up will also be summarized, along with the reasons for study discontinuations.

### 8.2. DEMOGRAPHIC AND OTHER BASELINE CHARACTERISTICS

Demographics and baseline characteristics (age, gender, ethnicity, race, weight, and height) will be summarized by dose level and overall for Phase 1 Dose Escalation.

#### 8.3. MEDICAL HISTORY

Medical history will be coded according to the Medical Dictionary for Regulatory Activities (MedDRA 17.0). Medical history will be listed by dose level or disease type, patient number, start date and end date. There is no imputation for dates for medical history.

### 8.4. OTHER BASELINE DISEASE CHARACTERISTICS

The cancer type (NSCLC, breast cancer, gastric cancer and other solid tumor), FGF/FGFR status (FGFR1 amplification, FGF19 amplification etc) by local genotyping assay) will be summarized by dose level and overall by dosing schedule.

Pre-study surgery and prior radiation therapy will be summarized by dose level and overall by dosing schedule. For pre-study surgery, the number and percentage of patients with biopsy, primary tumor removal, metastatic tumor removal, and other surgeries will be reported. For prior-radiation therapy, the number and percentage of patients with palliative and therapeutic radiation therapies will be presented in the summary table.

All prior anticancer therapies (adjuvant therapies, neoadjuvant therapies, therapies for advanced/metastatic disease, and maintenance therapies including prior FGFR inhibitor) will be summarized by dose level and overall by dosing schedule. The number of patients with 1, 2, 3 and >=4 prior regimens will be summarized for all anticancer therapies and for advanced/metastatic disease only.

Sponsor: Taiho Oncology, Inc. Protocol: TPU-TAS-120-101

Version: 3.3, Phase 1 Dose Escalation Only

## Statistical Analysis Plan

All collected information for cancer diagnosis, pre-study surgery, prior-radiation therapy, and prior anti-cancer therapy will also be listed.

#### 8.5. MEDICATION

Prior or concomitant medications will be collected from the time of informed consent through 30 days after administration of last dose of study medication.

Medications which started and stopped prior to the first dose of TAS-120 are considered as prior medications. Medications which started prior to the first dose of TAS-120 and continued into the treatment period are considered as prior and concomitant medications.

Medications with a start date from first dose of TAS-120 to 30 days after administration of the last dose of TAS-120 will be considered as concomitant medications.

Prior and concomitant medications will be coded according to World Health Organization (WHO) Drug Dictionary (WHODrug version March 2014) for Concomitant Medication. The concomitant medications will be summarized by ATC level 2 (Therapeutic Main Group) and ATC level 4 (Chemical/Therapeutic Subgroup) using the number and percentage of patients by dose level and overall. Medications will be sorted in descending order of frequency of ATC level 2 and ATC level 4 within ATC level 2 in the total column. A patient will be counted only once within each level of summation if the patient has taken a medication more than once.

All prior and concomitant medications will be listed.

Sponsor: Taiho Oncology, Inc. Protocol: TPU-TAS-120-101

Version: 3.3, Phase 1 Dose Escalation Only

## Statistical Analysis Plan

## 9. EFFICACY

#### **Solid Tumor Assessments**

Tumor assessments/imaging studies of the chest, abdomen, and pelvis (as clinically indicated) will be obtained at each time point listed below for all patients with solid tumors:

- Screening within 28 days prior to Day 1 of Cycle 1. Computed tomography scans obtained prior to the signed ICF may be used as the screening scan if they were obtained within 28 days of the first dose of TAS-120.
- At the end of every 2 cycles (± 7 days), up to Cycle 4.
- Following Cycle 4, at least after every 3 cycles or as clinically indicated.
- Within 2 weeks after discontinuation of TAS-120 treatment if the patient discontinued for reasons other than radiologic disease progression.

On-site tumor assessments will be performed by the investigator/local radiologist according to RECIST guidelines (version 1.1, 2009). Results of these assessments, including response for target and non-target lesions and appearance of new lesions, will be the basis for the continuation or discontinuation of TAS-120. Response definitions for target lesions, non-target lesions and overall responses are provided in the following Tables 5, 6, 7 and 8.

Table 5: Assessments for Target Lesions

TARGET LESIONS	
Lesion Response:	Definition:
Complete Response (CR)	The disappearance of all target lesions. Any pathological lymph nodes must have reduction in short axis to < 10 mm.
Partial Response (PR)	At least a 30% decrease in the sum of diameters of the target
	lesions, taking as a reference the baseline sum diameters.
Progressive Disease (PD)	At least a 20% increase in the sum of diameters of the target lesions, taking as a reference the smallest sum on study, including the baseline sum. In addition to the relative increase of 20%, the sum must also demonstrate an absolute increase of at least 5 mm. Definitive new lesion presence also indicates progression.
Stable Disease (SD)	Neither sufficient shrinkage to qualify for PR nor sufficient increase to qualify for PD, taking as a reference the smallest sum diameters while on study.

Sponsor: Taiho Oncology, Inc. Protocol: TPU-TAS-120-101

Version: 3.3, Phase 1 Dose Escalation Only

## Statistical Analysis Plan

Table 6: Assessments for Non-Target Lesions

NON-TARGET LESIONS		
Lesion Response:	Definition:	
Complete Response (CR)	Disappearance of all non-target lesions and normalization of tumor marker level. All lymph nodes must be non-pathological in size (< 10-mm short axis)	
Non-CR/Non-PD	Persistence of one or more non-target lesion(s) and/or maintenance of tumor marker level above the normal limits.	
Progressive Disease (PD)	Unequivocal progression of existing non-target lesions (see definition below).	

Table 7: Overall Response Assessment with Target Lesions

Target Lesions	Non-target Lesions	New Lesions	Overall Response
CR	CR	No	CR
CR	Non-CR/Non-PD or Not all evaluated	No	PR
PR	Non-PD or Not all evaluated	No	PR
SD	Non-PD or Not all evaluated	No	SD
Not all evaluated	Non-PD	No	Not evaluable
PD	Any	Yes or No	PD
Any	PD	Yes or No	PD
Any	Any	Yes	PD

Table 8: Overall Response Assessment without Target Lesions

Non-target Lesions	New Lesions	Overall Response
CR	No	CR
Non-CR/Non-PD	No	SD
Not all evaluated	No	Not evaluable
Unequivocal PD	Yes or No	PD
Any	Yes	PD

For Phase 1 Dose Escalation, only on-site tumor assessments will be conducted.

## 9.1. BEST OVERALL RESPONSE

The best overall response is the best response recorded from the start of treatment until progressive disease or the start of subsequent anticancer treatment.

Sponsor: Taiho Oncology, Inc. Protocol: TPU-TAS-120-101

Version: 3.3, Phase 1 Dose Escalation Only

## Statistical Analysis Plan

For patients with solid tumors, according to RECIST guideline (Version 1.1, 2009), to be assigned a status of PR or CR, changes in tumor measurements in patients with responding tumors must be confirmed at least 4 weeks after the criteria for response are first met. On the other hand, confirmation is not required for Phase 1 Dose Escalation. In the case of SD, measurements must have met the SD criteria at least once after study entry at a minimum interval of 6 weeks across the phases.

At the analysis stage, the best overall response will be assigned for each patient as the best response recorded from all time point responses recorded from the start of treatment. Confirmation of partial response and complete response will follow the confirmation process contained in the following table where the best two consecutive time points are considered. Best overall response both with confirmation of partial response and complete response and without confirmation of partial response and complete response will be summarized.

Earlier Response (not yet confirmed)	Later Response (confirmation)	Confirmed Response
Complete Response	Complete Response	Complete Response
Complete Response	No Complete Response or missing	Stable Disease
Partial Response	Complete Response or Partial Response	Partial Response
Partial Response	Stable Disease or Progressive Disease or missing	Stable Disease
Partial Response	Stable disease and then partial response (only one SD in between)	Partial Response
Stable Disease	n/a - no confirmation needed	Stable Disease
Progressive Disease	n/a - no confirmation needed	Progressive Disease

Sponsor: Taiho Oncology, Inc. Protocol: TPU-TAS-120-101

Version: 3.3, Phase 1 Dose Escalation Only

Statistical Analysis Plan

#### 9.2. OBJECTIVE RESPONSE RATE

The objective response rate (ORR) is defined as the proportion of patients who achieved best overall response of ≥ partial response (PR) in the Efficacy Population (CR or PR for solid tumor patients. ORR based on the Investigator's assessments will be summarized by disease type (for example NSCLC with FGFR1 amplification, breast cancer with FGFR1 amplification, gastric cancer with FGFR2 amplification, and other solid tumors with other alternative FGF/FGFR abnormality) by dosing schedule and overall. The corresponding 90% and 95% confidence intervals will be presented.

### 9.3. DURATION OF RESPONSE

Duration of response is derived for those patients with objective evidence of PR or CR. Duration of response is defined as the time from the first documentation of response (CR or PR) to the first documentation of objective progressive disease (PD) or death due to any cause.

After the first documentation of response, patients who are alive and progression free during the treatment period and follow-up will have their event time censored on the last tumor assessment date in the study treatment. For the purpose of final analyses for dose escalation phase, the last assessment date should be prior to the cut-off date of final analysis for which all patients either discontinue from the treatment or have sufficient follow-up (more than 6 months) from the date of the first day of treatment with TAS-120 of the last patient enrolled, whichever occurs first. For patients who start another anticancer treatment, their events should be censored at the last tumor assessment prior to the new treatment.

Time to response and Duration of response will be listed for Efficacy Population for Phase 1 Dose Escalation.

Sponsor: Taiho Oncology, Inc. Protocol: TPU-TAS-120-101

Version: 3.3, Phase 1 Dose Escalation Only

## Statistical Analysis Plan

### 10. SAFETY

The population used for safety analyses will be the Safety Population. Safety will be assessed on the basis of adverse event (AE) reports, clinical laboratory data, ECG parameters, physical examinations, vital signs and body weight, performance status, ophthalmological examination, and neurological examination.

## 10.1. EXTENT OF EXPOSURE

The actual dosage in the study for TAS-120 will be calculated for capsules and dosage. Since the patients may have different treatment periods, the average daily dose is defined as the dosage divided by actual dose duration, which is the sum of all cycle treatment period prior to the cut-off date of final analysis.

The cycles initiated and completed, extent of exposure (treatment duration), and total dosage for TAS-120 will be summarized by dose level and overall for Phase 1 Dose Escalation by dosing schedule.

Relative dose intensity (RDI) is defined as the ratio of the amount of drug actually administered to the amount planned in the study for TAS-120. The relative dose intensity from Day 1 of Cycle 1 is calculated in the following steps:

- 1. For each cycle, calculate the actual total dose administered in mg for TAS-120.
- 2. The total dose administered in mg is the sum of all cycle total doses administered in mg in the study.
- Total treatment duration in weeks for dose intensity calculation = (last dose date - first dose date +1) for QD; or (last dose date - first dose date +2) for QOD.
- 4. Weekly Dose Intensity = Total dose administered in mg divided by total treatment duration in weeks.
- 5. Relative Dose Intensity = Weekly Dose Intensity divided by the planned weekly dose in mg, which is the planned dose level in mg/day multiplied by 3.5 for QOD and multiplied by 7 for QD. The Relative Dose Intensity will be expressed in percentage.

Relative dose intensity will be summarized by dose levels and dosing schedule for cycle 1 and for all cycles.

Sponsor: Taiho Oncology, Inc. Protocol: TPU-TAS-120-101

Version: 3.3, Phase 1 Dose Escalation Only

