QOD	3 times a week (Monday, Wednesday, and Friday) dosing
QTc	Corrected QT Interval
QTcB	Bazett's Correction of QT Interval
QTcF	Fridericia' Correction of QT Interval
RAUC	Accumulation ratio calculated based on AUCO-last
RBC	Red Blood Cell
RCmax	Accumulation ratio calculated based on Cmax
RDI	Relative Dose Intensity
RECIST	Response Evaluation Criteria in Solid Tumors
RP2D	Recommended Phase 2 Dose
RSQ	R-Square
SAE	Serious Adverse Event
SAP	Statistical Analysis Plan
sCR	Stringent complete response
SD	Stable Disease
SE	Standard Error
SFLC	Serum free light chain
SI	Standard International System of Units

Sponsor: Taiho Oncology, Inc. Protocol: TPU-TAS-120-101

Version: 3.3, Phase 1 Dose Escalation Only

Abbreviation	Description
SOC	System Organ Class
SOP	Standard Operating Procedure
SPEP	Serum Protein Electrophoresis
TEAE	Treatment Emergent Adverse Event
TLF	Table, Listing and Figure
TOI	Taiho Oncology Inc.
TPC	Taiho Pharmaceutical, Co., Ltd.
T 1/2	Half-life time
T max	Time to reach maximum concentration in plasma
ULN	Upper Limit of Normal
UPEP	Urine Protein Electrophoresis
Vd/F	Apparent volume of distribution
WBC	White blood cell
WHO	World Health Organization

Sponsor: Taiho Oncology, Inc. Protocol: TPU-TAS-120-101

Research\*

Version: 3.3, Phase 1 Dose Escalation Only

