### 4.5. ADMINISTRATION OF STUDY MEDICATION

Each treatment cycle is 21 days in duration. During Phase 1 Dose Escalation, TAS-120 is given to patients in each cohort of escalating doses to determine the MTD.

All patients receive TAS-120 at the assigned dose, orally, once a day, 3 times a week (Monday, Wednesday, and Friday) [QOD] or continuously (once daily dosing [QD]) in 21-day treatment cycles. TAS-120 is taken with a glass of water on an empty stomach (2 hours after and 1 hour before a meal).

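### Dose Escalation SAP 10.1 labels treatment duration as weeks but computes it in days, so relative dose intensity comes out 7-fold too low if coded literally; the QOD terms also need reconciling

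*SAP*

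**What the plan says.** All of the following is in the Dose Escalation SAP. Section 10.1 first gives the principle: "Relative dose intensity (RDI) is defined as the ratio of the amount of drug actually administered to the amount planned in the study for TAS-120". A patient who takes every planned dose should therefore have an RDI of 100%.

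The calculation then runs in five steps. Steps 1 and 2 add up the milligrams taken. Step 3 defines the duration: "Total treatment duration in weeks for dose intensity calculation = (last dose date - first dose date +1) for QD", and for the other schedule "last dose date - first dose date +2) for QOD". Step 4 is "Weekly Dose Intensity = Total dose administered in mg divided by total treatment duration in weeks". Step 5 divides that by the planned weekly dose, "which is the planned dose level in mg/day multiplied by 3.5 for QOD and multiplied by 7 for QD", and expresses the result as a percentage. RDI is to be summarised by dose level and schedule, for Cycle 1 and for all cycles.

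Two other places bear on this. Section 7.2.5 uses the same expression as the QD formula with no mention of weeks: "The overall treatment duration is defined as last dose date - first dose date+1". The glossary defines QOD as "3 times a week (Monday, Wednesday, and Friday) dosing", and section 4.5 describes the same schedule.

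**The concern.** The label in step 3 says weeks, but the expression beside it counts days. Step 4 therefore yields milligrams per day under the name of a weekly intensity, and step 5 divides that by a true weekly dose. The units do not cancel.

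At stake is the exposure table by dose level and schedule. If the text is coded as it stands, every column would suggest that patients took about one seventh of the planned drug. The SAP also relies on independent programming with electronic comparison (section 18). Two programmers who both follow the text would agree on the wrong figure. If only one adds the conversion, the SAP has no formula that settles the mismatch.

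The QOD column has a second problem. The step 5 multiplier of 3.5 doses a week does not match a schedule of 3 doses a week, and no unit label would alert a programmer to it.

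**Working it through.** The SAP states no numerical RDI to reproduce. The benchmark is its own definition, administered over planned, which is 100% for full dosing.

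**Inputs**
- Duration D, from step 3: last date − first date + 1 (QD) or + 2 (QOD), in days.
- Planned weekly dose, from step 5: 7 × L (QD) or 3.5 × L (QOD), where L is the dose level.
- Cycle length 21 days (section 4.5); QOD on Monday, Wednesday and Friday (glossary and section 4.5).
- QD example level 20 mg (listed in section 7.1). L cancels, so the choice does not matter.

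**General result.** With T the total mg and W the planned weekly dose, the text gives (T/D)/W. With the duration in weeks it is (T/(D/7))/W = 7 × (T/D)/W. The ratio is 7 for every patient in both schedules.

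**QD, 20 mg, one 21-day cycle, no missed dose**
- T = 20 × 21 = 420 mg; D = 21.
- As written: 420/21 = 20; 20/(20 × 7) = 14.3%.
- With D/7 = 3 weeks: 420/3 = 140; 140/140 = 100%.
- Both results are the same at 42, 84 and 365 days.

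**QOD, Monday start, Friday last dose, 3 weeks, all 9 doses taken**
- First dose day 1, last dose day 19; D = 19 − 1 + 2 = 20.
- As written: (9L/20)/(3.5L) = 12.9%.
- With D/7: (9L × 7/20)/(3.5L) = 63/70 = 90.0%.

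**Why QOD is still short of 100%.** Over w such weeks there are 3w doses and D = 7w − 1. After division by 7, RDI = (3w × 7)/((7w − 1) × 3.5) = 6w/(7w − 1).

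| Weeks | Doses | D (days) | As written | D/7, multiplier 3.5 | D/7, multiplier 3 |
|---|---|---|---|---|---|
| 3 | 9 | 20 | 12.9% | 90.0% | 105.0% |
| 6 | 18 | 41 | 12.5% | 87.8% | 102.4% |
| 12 | 36 | 83 | 12.4% | 86.7% | 101.2% |
| 52 | 156 | 363 | 12.3% | 86.0% | 100.3% |

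The fifth column tends to 6/7 = 85.7%. The last column shows that changing the multiplier to 3 while keeping the +2 offset overshoots instead.

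The +2 and the 3.5 do fit strict alternate-day dosing. There, n doses span D = 2(n − 1) + 2 = 2n days, and (n × 7/(2n))/3.5 = 100%. They do not fit Monday/Wednesday/Friday dosing, where the Friday-to-Monday gap is three days.

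**The case against.** The strongest reply is that the intended meaning is plain. Steps 3 and 4 both name weeks, and the section opens with the correct definition of RDI. Section 18 requires independent coding and review of all outputs by senior statistical and programming staff, who would probably notice a table with full dosing at about 14%. Section 10.1 also defines an average daily dose, which offers a cross-check. This reply stands as far as it goes. The documents contain no output, so they do not show that a wrong table was produced. It does not make the formula right, and it gives no protection against the 3.5 multiplier.

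A lost division sign in the PDF text cannot be strictly excluded, because this line has lost its step number. It would have to be missing from both the QD and the QOD expressions, and nothing in the text suggests that. The source file will settle it.

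A reader might infer that the error undermines the selection of 20 mg QD. The documents do not support that. The MTD is defined by the proportion of patients with a DLT in Cycle 1 (Dose Escalation SAP 4.1.1). Protocol 5.4 rests the choice on DLT counts: 3 of 9 at 24 mg and none of 5 at 20 mg. RP2D selection draws on safety data in general (SAP 4.1), but no decision rule cites RDI, and dose reductions, holds and discontinuations due to AEs are summarised separately. A constant factor of 7 also leaves comparisons between dose levels within a schedule unchanged.

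A reader might also think that the 80% dosing requirement for the DLT-evaluable population (SAP 6.2) would fail under this formula. Section 6.2 refers to planned medication administered and does not invoke the section 10.1 calculation.

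**Conclusion.** The rule is wrong as written. If coded literally, RDI is too low by a factor of exactly 7 in both schedules: 14.3% in place of 100% for any fully dosed QD patient, and 12.9% for a fully dosed QOD patient at 3 weeks. Correcting the unit alone makes QD right. It leaves fully dosed QOD patients at 90.0% at 3 weeks, drifting towards 85.7%, so a QD-to-QOD comparison would still be distorted.

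The consequence is limited to a descriptive exposure table for a completed part of the study. The Expansion and Phase 2 SAPs (section 6.5.1.1 in each) divide the number of doses by the number of days and do not have this unit error.

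The QOD figures assume a Monday start, a Friday last dose and no missed doses. The QD figure needs only full dosing. Whether any reported table is affected cannot be told from the documents.

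**What to change.** 1. In step 3, divide both expressions by 7, so that the quantity is in weeks as labelled.
2. Reconcile the QOD terms in steps 3 and 5, the +2 offset and the 3.5 multiplier, with the stated schedule of three doses a week. They have to be changed together. A simple way is to drop the weekly form for QOD and use total mg administered divided by (planned dose level × number of scheduled QOD doses in the treatment period) × 100. In the 3-week example this is 9L/9L = 100%.
3. Add one worked example per schedule to the SAP, each showing 100% for a fully dosed patient.
4. Confirm which formula produced any RDI table already reported. If it was the literal one, or if it used the 3.5 multiplier for QOD, re-run and correct the table.

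The cost is a few lines in one SAP section, a check of the existing program and, at most, a re-run of the RDI summaries. No new data are needed.
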